IV. Research Design

1. Research Subjects

who were diagnosed with retained products of pregnancy by ultrasound at outpatient clinics of various research units between June 2022 and June 2024, and who met the inclusion criteria but did not meet the exclusion criteria, were all enrolled consecutively.

Inclusion criteria: age 18-45 years, clinical diagnosis of retained products of conception, and ultrasound showing a lesion with a maximum diameter ≥ 0.5 cm.

Exclusion criteria: 1) Active bleeding requiring immediate surgical intervention; 2) Significant infection; 3) Severe organ dysfunction, including coagulation disorders.

Note: Patients with cervical tissue impacted in the cervical canal who have undergone clamping treatment and do not meet the exclusion

criteria can be included in this study;

2. Grouping

Because there is currently no unified treatment plan for retained products of pregnancy in uterus, the timing of active surgical evacuation versus expectant management until the planned surgery remains controversial, and the optimal timing for surgical evacuation is not uniform. In clinical practice, physicians, based on fully informed consent, choose active surgical treatment or expectant management according to the patient's wishes, and perform surgery when necessary. This study does not interfere with patient treatment; it only designs and collects relevant data in advance. No additional examinations or tests are performed on patients during the study process, and all procedures are conducted according to standard clinical practice. After treatment, patients are divided into an active surgical group and an expectant management group based on their chosen treatment plan, and data are statistically analyzed.

3. Sample size and allocation

The sample size was determined based on the incidence of intrauterine adhesions, the primary outcome measure. According to previous research results, the intrauterine adhesion rate in the expected group was 5.38%, and the intrauterine adhesion rate in the patients undergoing active surgery was 14.29%. The Type I error was 0.05, the power was 90%, and the sample size was calculated using PASS to obtain a total of 460 cases. Based on a 20% follow-up dropout rate, the sample size was calculated to be 576 cases. It is expected that 600 cases will be included, with 120 cases from the lead institution and an average of 40 cases from the other 12 research institutions.

4. Research Process

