Postoperative follow-up indicators: β -HCG on the 3rd day after surgery (once a week thereafter until normal), complete blood count (days 1 and 3), CRP, procalcitonin (not mandatory); if necessary, transvaginal ultrasound on the 2nd-3rd day after surgery. A 4D ultrasound is performed on days 16-24 of the third menstrual period after surgery to assess the uterine cavity and blood flow (report templates are available, mainly assessing damage to the endometrium).

Management of retained products of conception after surgery: If ultrasound shows that the diameter of the retained products of conception is less than 0.5 cm, an artificial cycle is given, and a follow-up color Doppler ultrasound and β -HCG test are performed after the next menstrual period to determine whether further surgery is needed; if ultrasound shows that the diameter of the retained products of conception is greater than 0.5 cm, the patient is put back into the expectant management process and managed as an outpatient.

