4.3 Data collection process

4.3.1 Outpatient data collection: The patient's first outpatient visit data and each outpatient follow-up visit data include main symptoms, blood β -HCG, ultrasound and infection-related indicators.

4.3.2 Data collection for inpatient surgery includes: preoperative symptoms; serum β -HCG, ultrasound and infection-related indicators; surgical data; and postoperative medication.

4.3.3 Follow-up after surgical treatment:

(1) If the ultrasound examination 3 days after the operation shows no pregnancy residue or the diameter of the residue is less than 0.5cm, follow up by phone or WeChat 1 month later to ensure that the patient's menstruation is over and to have a follow-up examination of β -HCG, ultrasound and other indicators at the outpatient clinic to determine whether the treatment has ended.

(2) If the ultrasound examination on the 3rd day after surgery shows that the

diameter of the retained pregnancy tissue is greater than 0.5cm, follow up by phone or WeChat half a month later to ensure that the patient goes to the outpatient clinic on schedule for β -HCG, ultrasound and infection indicators, and to determine the subsequent treatment plan.

4.3.4 Data collection after treatment: Menstrual flow, ultrasound findings of intrauterine adhesions, and endometrial thickness were collected during outpatient follow-up examinations three times after the end of treatment.

4.3.5 Data collection on reproductive outcomes: For patients who wish to have children, follow-up by telephone will continue every 3 months. If the patient has not become pregnant after 1 year of follow-up, the follow-up will be terminated. If the patient becomes pregnant within 1 year, follow-up will continue until the pregnancy is terminated, including whether there is spontaneous abortion, premature birth, full-term birth, stillbirth, or stillbirth.

5. Data Collection

5.1 General information: age, parity, number of previous intrauterine procedures, history of intrauterine adhesions, occupation, and education level.

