5.2 Preoperative data on retained products of pregnancy: gestational age at termination; time of termination; serum β -HCG; imaging data (including ultrasound and MRI: uterine size, distance from the internal cervical os to the fundus, location of the retained products of pregnancy, maximum diameter, blood flow, presence of arteriovenous fistula (blood flow grade 1-6 in the retained products of pregnancy and surrounding uterine wall on color Doppler ultrasound), presence of placenta accreta, presence of intrauterine adhesions, uterine septum, uterine fibroids, adenomyosis. For the expectant management group, complete blood count, serum β -HCG, CRP, and ultrasound data from each follow-up examination should be collected.

5.3 Preoperative routine examination data : routine vaginal discharge test, HPV/TCT, complete blood count, liver and kidney function tests, electrolytes, coagulation function tests, thyroid function tests, serum β -HCG, anti-Müllerian hormone test, pre-transfusion examination, electrocardiogram, chest X-ray, 3D color Doppler ultrasound of the uterus and bilateral adnexa, and other relevant examinations. If a 3D ultrasound has been completed within one week in the outpatient clinic, it does not need to be repeated during hospitalization.

5.4 Surgical data: Date of surgery; depth of uterus; location and size of the gestational sac; operation time (from the start of the distension procedure to the withdrawal of the endoscope); amount of intraoperative blood loss; whether there is any retained gestational sac after surgery; clarity of the surgical field; volume of distension fluid in and out; whether there is a decrease in blood oxygen saturation;

whether complications such as uterine perforation, acute left heart failure, or gas embolism occur.

5.5 Postoperative follow-up data: serum β -HCG, complete blood count, CRP, procalcitonin (not required), ultrasound to check for retained products of conception, and if so, record the maximum diameter of the retained products.

5.6 Three months after treatment , outpatient follow-up data will be collected, including menstrual flow, ultrasound findings of intrauterine adhesions, endometrial condition, whether intrauterine adhesion surgery was performed, and intrauterine adhesion score.

5.7 Pregnancy outcome data collection: pregnancy rate after 1 year of trying to conceive ; miscarriage rate, premature birth rate, full-term birth rate, stillbirth rate, and stillbirth rate in subsequent pregnancies.

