
6. Efficacy evaluation

6.1 Main observation indicator: Incidence of intrauterine adhesions.

6.2 Secondary observation indicators: reoperation clearance rate; incidence of active bleeding and infection during expectant treatment in the expectant treatment group; pregnancy rate, live birth rate, and miscarriage rate one year after treatment.

7. Safety Assessment

7.1 Safety indicators: the expected probability of active bleeding and infection during treatment.

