9.2 Bias Control

The clinical research process strictly follows standard operating procedures, clearly defining pre-clinical research training, quality control, and other aspects.

All research institutions conducted their studies concurrently, implementing a unified clinical research protocol.

Before a clinical study begins, training should be provided on the clinical study protocol and standard operating procedures, especially on ultrasound report content, perioperative management, surgical procedure specifications, and surgical records.

The clinical research process includes monitoring and accountability procedures.

By controlling bias through the above process, research error can be reduced.

9.3 Pre-clinical training: Before a clinical trial, standard operating procedures should be developed in accordance with the clinical trial protocol, and all researchers participating in the trial should be trained on the clinical trial protocol, standard operating procedures, etc., to ensure consistency in all procedures during the trial; training should also be provided on ultrasound reporting standards, surgical operation standards, etc.; and training plans and records should be kept.

9.4 Research Quality Control: All researchers participating in the clinical trial should complete training on the clinical trial protocol, standard operating procedures, and other relevant documents, and strictly adhere to the provisions of these documents during the trial. Training should also be provided on ultrasound reporting standards and

surgical procedure standards. The lead institution will assign qualified monitors to conduct on-site monitoring visits to the clinical trial facility at different stages of the clinical trial to ensure that the clinical trial is conducted in accordance with relevant laws and regulations, the clinical trial protocol, and standard operating procedures.

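### The primary adhesion outcome has no single instrument or time point and no stated masking of the ultrasound reader, so detection can differ between the groups

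*Protocol*

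**What the plan says.** The primary outcome is stated in one line of the Protocol: "6.1 Main observation indicator: Incidence of intrauterine adhesions". Section 6.1 attaches no instrument, criterion or visit to it.

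Three other places describe data from which it could be read:

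- Section 4.3.4: "Menstrual flow, ultrasound findings of intrauterine adhesions, and endometrial thickness were collected during outpatient follow-up examinations three times after the end of treatment".
- Section 5.6, for the visit three months after treatment: menstrual flow together with "ultrasound findings of intrauterine adhesions, endometrial condition, whether intrauterine adhesion surgery was performed, and intrauterine adhesion score".
- Section 4.2.3, postoperative follow-up: "A 4D ultrasound is performed on days 16-24 of the third menstrual period after surgery to assess the uterine cavity and blood flow".

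No second-look hysteroscopy is scheduled for either group. Section IV.2 says: "No additional examinations or tests are performed on patients during the study process, and all procedures are conducted according to standard clinical practice". The same section forms the groups from the treatment that patients choose.

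Section 4.2.3 also covers women with residue above 0.5 cm after surgery: "the patient is put back into the expectant management process and managed as an outpatient". Section 4.1.2 foresees expectant patients who expel the tissue and may need no operation.

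Section 9.2 lists standard procedures, training, concurrent conduct under one protocol, and monitoring. It concludes: "By controlling bias through the above process, research error can be reduced". Masking of whoever reads the ultrasound is not among the measures.

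**The concern.** A comparison of adhesion rates is fair only if adhesions are looked for in the same way, at the same time and with the same readiness to call them in both groups. The Protocol does not secure this.

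A centre could count a case from any of three post-treatment ultrasounds, from the three-month ultrasound alone, or from adhesion surgery or a score. Surgery gives a direct view of the cavity only in the women who have it. The one scan with a precise cycle window has no start date for a subset that exists only in the expectant group. The ultrasound call is a judgement, and nothing in the plan keeps the reader unaware of the group. Expectant women are scanned every 2-3 weeks while waiting (4.1.2), so a reader at the same clinic may recognise them.

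The tests in Section 8 (chi-square or Fisher) cannot tell a difference in detection from a difference in adhesions. Nor can this be left to an analysis plan, because an analysis plan cannot mask a scan that has already been read.

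**Working it through.** **1. The plan's own figure.** Inputs from Section IV.3 are 14.29% (active surgery) versus 5.38% (expectant), alpha 0.05 and power 90%. I assume a two-sided test and 1:1 allocation, which are not stated. With unpooled variance:

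n per group = (1.960 + 1.282)² × (0.1429 × 0.8571 + 0.0538 × 0.9462) / 0.0891² = 230 after rounding up, so 460 in total.

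With 20% dropout, 230 / 0.80 = 287.5, so 288 per group and 576 in total. Both stated figures reproduce. The sample size is not the problem. The planned difference is 14.29 − 5.38 = 8.91 points.

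**2. The passages side by side.**

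- Instrument: 4.3.4 and 4.2.3 give ultrasound only. 5.6 gives ultrasound plus adhesion surgery and a score of unstated method. 6.1 gives none.
- Time: 4.3.4 has three examinations after the end of treatment, 5.6 has three months after treatment, and 4.2.3 has the third menstrual period after surgery. 6.1 gives none.
- Women without an operation: covered by the wording of 4.3.4 and 5.6, but not by 4.2.3.

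**3. Size of the further-procedure route, if findings at further procedures are counted.** The documents give no sensitivities or repeat rates, so all inputs here are assumptions: true risk p = 15% in both groups, ultrasound sensitivity s = 0.5 to 0.8, hysteroscopy detects every adhesion, no false positives, and a further hysteroscopy in r = 20-30% of active versus 5-10% of expectant women.

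Detected rate = p × [r + (1 − r) × s], so the gap = p × (r_active − r_expectant) × (1 − s).

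- Largest gap (s = 0.5, 30% versus 5%): 15 × 0.65 = 9.75% versus 15 × 0.525 = 7.88%, a gap of about 1.9 points.
- Smallest gap (s = 0.8, 20% versus 10%): 15 × 0.84 = 12.60% versus 15 × 0.82 = 12.30%, a gap of 0.3 points.

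Against 8.91 points this is 0.3 / 8.91 = 3% to 1.875 / 8.91 = 21%.

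**4. Illustration of differential reading.** Sensitivity (Se) and specificity (Sp) are again assumed. The apparent rate is p × Se + (1 − p) × (1 − Sp). Take a true rate of 10% in both groups and 230 women per group. The chance of a significant result favouring expectant management should then be 2.5%.

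- Se 0.90 (active) versus 0.70 (expectant), Sp 0.95 in both: 13.5% versus 11.5%, chance about 10%.
- Se 0.80 in both, Sp 0.93 versus 0.97: 14.3% versus 10.7%, chance about 21%.

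These show that modest reading differences could matter more than the further-procedure route. They do not estimate what will happen in this study.

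**The case against.** The strongest reply is that the Protocol does standardise the ultrasound. Section III and Section 9.2 require training in measurement and report content, and 4.2.3 supplies a report template. The three follow-up descriptions may also be meant as one visit, since the third menstrual period after an operation falls at roughly three months. This stands as partial mitigation. But training and templates do not hide the group, the texts do not say that they describe one visit, and the scan in 4.2.3 still has no date for women without surgery.

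A reader might infer that the primary outcome rests on hysteroscopic findings available only in women who have another procedure. The documents do not support that. Nowhere is the score said to be hysteroscopic, or said to count towards 6.1. Repeat removals for residue happen during treatment, before the post-treatment data of 4.3.4 and 5.6. Adhesions seen at such an operation go into the operative record (4.2.2), and no section carries them into the primary outcome. What the text supports is that the outcome is undefined.

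A reader might also infer that the bias must favour expectant management. The hypothesis stated just before Section II expects fewer repeat operations after waiting, and readers may know it, so that direction is plausible. Against it, expectant women who reach the planned timing also have hysteroscopy, they have more scans while waiting, and a further procedure can refute a false-positive ultrasound as well as reveal a missed adhesion.

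That the reader is unmasked is inferred from the list in 9.2; it is not stated.

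**Conclusion.** The point holds in a limited form. The primary outcome has no single instrument or time point, the passages that feed it differ, one scheduled scan leaves out women without surgery, and no masking of the reader is listed. Following the plan as written, detection can differ between self-selected groups. The direction is plausibly towards expectant management but not certain.

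The further-procedure route alone is worth about 0.3 to 1.9 points of the planned 8.91, and only if findings at further procedures are counted and the assumed inputs apply. Unmasked reading could be the larger source, but its size is unknown. It is tempting to add an assumed reader shift of 2 to 3 points, reach about 2.3 to 4.9 points, and conclude that a quarter to a half of the planned difference could be spurious. Most of that total would be the assumed shift, for which the documents offer no basis.

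This should be corrected because the primary comparison depends on it and the remedy is cheap. It does not invalidate the study.

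**What to change.** - In 6.1, define a primary case as adhesions on the ultrasound at the three-month post-treatment visit of 5.6. Time the visit from the end of treatment for every woman, with or without surgery, and use one report template and one set of criteria in both groups.
- Reconcile 4.3.4 and the 4D scan in 4.2.3 with that definition.
- Report adhesions found only at a later procedure, adhesion surgery, and the adhesion score (with its method stated) as separate secondary or sensitivity results.
- Issue the request for that scan without treatment group or operative details. Where the existing rota allows, have it done by a trained sonographer who did not perform the woman's waiting-period scans. Add both measures to 9.2.

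The cost is a few sentences and a plain request form. The visit is already planned for all women, so no examination or staff is added. Masking helps only scans still to be done. Some adhesions seen only at a procedure will leave the primary count, and masking will be incomplete at small centres where one sonographer covers the clinic.

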7.2 Reporting and follow-up of adverse events and serious adverse events

Possible adverse events: active bleeding; infection; the following are considered serious adverse events: massive bleeding requiring emergency interventional treatment; severe infection with systemic toxicity symptoms or pelvic abscess are considered serious adverse events.

Any adverse events or serious adverse events that occur during the research process must be reported to the responsible unit and other collaborating research units within 3 days, along with an analysis of the causes.

8. Statistical Analysis: SPSS 26.0 software was used to process the data .

Normally distributed measurement data were expressed as ($\bar{x} \pm s$), and t-tests were used for comparisons between two groups; analysis of variance was used for comparisons among multiple groups. Non-normally distributed measurement data were expressed as the median, and a nonparametric rank-sum test was used. Count data were expressed as χ^2 . The χ^2 test or Fisher's test was used. $P < 0.05$ was considered statistically significant.

9. Clinical Research Management

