Hysteroscopic electrosurgical resection of pregnancy has a short operation time and less intraoperative bleeding. Direct visualization during the operation can avoid extensive curettage of the endometrium and significantly reduce complications such as incomplete curettage. For patients with uterine malformations, it can avoid blind curettage that misses part of the uterine cavity and leads to incomplete curettage, and can also treat uterine malformations simultaneously under hysteroscopy. However, the electrosurgical ring brings thermal radiation damage during treatment, which can easily damage the surrounding endometrial tissue, increase the risk of intrauterine adhesions, and in severe cases, damage the basement membrane or even the deep myometrium, leading to abnormal placental implantation in subsequent pregnancies [17].

Hysteroscopic cold knife removal of pregnancy tissue has no electrothermal damage, which is beneficial to protect the endometrium and reduce the risk of intrauterine adhesions and infertility after curettage. It is increasingly widely recognized [18]. Literature [19] compared the treatment of intrauterine diseases with electrocautery system and cold knife system and found that the latter reduced the incidence of intrauterine adhesions by 90% after surgery and could effectively avoid damage to the surrounding endometrial tissue by electroradiation. At present, the application of giant cold knife instruments is becoming more and more widespread. For example, the 4mm (i.e. 12 Fr) spoon forceps can directly remove residual tissue under vision, which has a great advantage over traditional micro forceps. The hysteroscopic shaving system uses a blunt head and side window operation to remove lesion fragments while removing lesions, avoiding repeated entry and exit from the uterine cavity. Its operation time is significantly shorter than that of the electrocautery group,

and the incidence of serious complications such as uterine perforation and massive bleeding is significantly reduced. At the same time, it avoids electrothermal radiation damage and significantly reduces intrauterine adhesions. However, it is important to emphasize the correct use method when using it, especially to avoid damage caused by excessive cutting of the endometrium.

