In summary, hysteroscopic surgery is the most effective treatment for patients with large retained products of conception. However, due to the large size of the lesion, especially in cases of a large uterus, high serum HCG levels, and rich blood supply, the likelihood of needing repeat or even multiple curettage procedures increases, raising the risk of infection and endometrial damage. This not only increases costs but also leads to intrauterine adhesions and infertility. For these patients, appropriate drug treatment or expectant management followed by hysteroscopic surgery may be a wise choice and warrants further clinical research. Drug treatment and expectant management are also effective and safe under certain conditions for managing retained products of conception. Previous studies have shown that expectant management can allow some patients to expel the retained products of conception spontaneously, avoiding curettage; when curettage is performed 1-3 months after termination of pregnancy, serum HCG levels drop to low levels, reducing the difficulty of hysteroscopic surgery, intraoperative risks, and the likelihood of repeat surgery, as well as the incidence of postoperative intrauterine adhesions. Therefore, we propose the following scientific hypothesis: for patients with retained products of conception, in the absence of infection and active bleeding, expectant management should be maintained until the appropriate surgical time, thereby reducing the likelihood of repeat surgery and protecting the endometrium. To verify this scientific hypothesis, we designed a prospective, observational, multicenter, real-world study. The study subjects were patients with retained products of conception without bleeding or infection. Under the guidance of the physicians in the treatment group and with full informed consent, patients were selected according to their wishes to either the active surgery group (control group) or the expectant management group (study group). The diagnosis and treatment procedures were standardized, and detailed clinical data were collected to explore the optimal treatment strategy for retained products of conception, especially the best treatment plan for the protection of fertility.

II. Research Objectives

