
All surgeons are gynecologists with extensive experience in hysteroscopic surgery who have received standardized training . **The following key points should be recorded during the procedure:** uterine depth; location and size of the pregnancy

tissue; operative time (from the start of uterine distension and insertion of the endoscope to its withdrawal); intraoperative blood loss (a routine blood test is recommended on the first postoperative day) ; whether there is any retained pregnancy tissue after the procedure; clarity of the surgical field; volume of distension fluid intake and output; whether there is a decrease in blood oxygen saturation; and whether complications such as uterine perforation, acute left heart failure, or gas embolism occur.

Note: 1) Hysteroscopic resection with a cold knife is recommended for removal of the pregnancy tissue. For surgical techniques, please refer to the surgical video. Link: https://pan.baidu.com/s/1F4RE6_g-gNtXsrhTs2B2UQ?pwd=1234

Extraction code: 1234.

Research institutions may choose ultrasound-guided curettage, micro-cold knife technique , intrauterine tissue excision system , or electrosurgical resection, depending on their own conditions, and should record the surgical method and instruments used.

2) If the surgical field is obstructed due to massive bleeding or other reasons, it is not essential to remove the pregnancy tissue. The primary goal is to ensure surgical safety and protect the endometrium. The procedure can be performed in stages.

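### The primary adhesion rate is compared between self-selected groups with an unadjusted chi-square or Fisher test, and the bias-control section does not address confounding

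*Protocol*

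**What the plan says.** **Allocation.** Protocol section IV.2 (Grouping) says that physicians, after informed consent, "choose active surgical treatment or expectant management according to the patient's wishes, and perform surgery when necessary". It continues: "After treatment, patients are divided into an active surgical group and an expectant management group based on their chosen treatment plan". Nothing is randomised or matched.

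**Aim and outcome.** Section II is comparative and causal in intent: waiting is expected to lower adhesion incidence relative to active surgery. Section 6.1 makes adhesion incidence, a yes/no outcome, the main indicator.

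**Analysis.** Section 8 lists t-tests, analysis of variance, a rank-sum test and, for count data, the chi-square "test or Fisher's test was used", at P < 0.05. It names no regression, matching, weighting, stratification or centre term.

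**Bias control.** Section 9.2 lists standard procedures, concurrent conduct under one protocol, training and monitoring, and concludes: "By controlling bias through the above process, research error can be reduced".

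**Data available.** Section 5.1 collects "age, parity, number of previous intrauterine procedures, history of intrauterine adhesions, occupation, and education level". Section 4.3.1 collects HCG, ultrasound and infection indicators from the first outpatient visit on. Section 5.2, headed as preoperative data, adds gestational age, time of termination and detailed imaging. None of these is assigned to the group comparison.

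**Centre.** Section 4.1.2 lets hospitals adjust the surgical timing parameters. Note 1 to section 4.2.2 says "Research institutions may choose ultrasound-guided curettage" or several other techniques, according to their own conditions.

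**The concern.** When patients and physicians choose the strategy, the groups can differ at the outset in features that also drive adhesions. A crude two-by-two test then mixes the effect of timing with the effect of those features. Training and monitoring reduce measurement and conduct error, but they do not balance the groups.

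The protocol itself describes the mechanism. The last background paragraph before section II says that large lesions, especially with a large uterus, high HCG and rich blood supply, make repeat curettage and hence adhesions more likely. It then suggests drug treatment or waiting before surgery for these same patients. If clinicians act on that, higher-risk women gather in the expectant group. Other forces, such as prior procedures or a patient's wish for quick resolution, could push the other way.

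At stake is whether the P-value and rate difference for the primary outcome can bear on the aim in section II at all.

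**Working it through.** **Step 1: the plan's own sample size.** Inputs from section IV.3: 14.29% (active), 5.38% (expectant), alpha 0.05, power 90%, total 460, and 576 after 20% dropout. Unpooled two-sided formula at 1:1:

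n = (1.960 + 1.2816)² × (0.1429×0.8571 + 0.0538×0.9462) / (0.1429 − 0.0538)² = 10.507 × 0.17339 / 0.007939 = 229.5, so 230 per group and 460 in total.

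Dropout: 230/0.8 = 287.5, so 288 per group and 576 in total. Both figures reproduce. The arithmetic is sound, and it is the arithmetic of a crude comparison. The expected number of adhesions is 230 × (0.1429 + 0.0538) = 45.

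**Step 2: false benefit (assumed inputs, not in the documents).** Suppose timing has no effect. One baseline factor multiplies adhesion risk by RR and is present in a share a of active and e of expectant patients. With baseline risk r, the rates are r[1 + (RR−1)a] and r[1 + (RR−1)e]. Set the average of the two rates to 10%, close to the mean of the planning rates, (14.29 + 5.38)/2 = 9.8%.

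For RR = 3, a = 60%, e = 30%: the rates are 2.2r and 1.6r, and 1.9r = 10% gives r = 5.26%. That is 11.6% vs 8.4%, a spurious difference of 3.2 points against the planned 8.9.

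**Step 3: hidden benefit (assumed).** Let the planned effect be real and swap the prevalences, so the factor is commoner in the expectant group. Active stays at 14.29%. Expectant becomes 5.38% × 2.2/1.6 = 7.4%.

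**Step 4: rejection rates.** Two-sided pooled two-proportion test at 5%, 230 per group, by enumerating the two binomial distributions. With no imbalance, the test rejects 5% of the time under no effect and has 91% power at the planned effect (90% by the normal approximation).

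| RR | Prevalence in the two groups | Rates, no timing effect | Rejection | Power if reversed and effect real |
|---|---|---|---|---|
| 2 | 50% vs 40% | 10.3% vs 9.7% | 6% | 88% |
| 2 | 50% vs 30% | 10.7% vs 9.3% | 8% | 83% |
| 3 | 50% vs 30% | 11.1% vs 8.9% | 13% | 77% |
| 3 | 60% vs 30% | 11.6% vs 8.4% | 20–21% | 67% |

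A second set of assumptions (overall risk 9.8%, confounder odds ratio 2 to 4, prevalence from 60% vs 40% up to 80% vs 20%) gives rejection between 7% and 66%, with spurious differences of 1.2 to 6.6 points.

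**Step 5: precision cost of adjustment.** If covariates explain a share R² of group membership, the evaluable total needed is roughly 460/(1 − R²). For assumed R² of 0.05, 0.10 and 0.20 this is 485, 512 and 575. The planned 600 patients with 20% dropout leave 600 × 0.8 = 480.

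**The case against.** **A SAP may supply the adjustment.** Section 8 does not label a primary analysis or forbid an adjusted one, and covariate models are often left to a SAP. But the protocol is not silent here. It states an unadjusted test for this type of outcome and presents a bias-control section as the answer to bias. The point stands.

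**Partial controls exist.** Enrolment is consecutive, and section IV.1 excludes active bleeding needing immediate surgery, significant infection and severe organ dysfunction, including coagulation disorders. This narrows the population. It does not balance lesion size, HCG, blood flow or adhesion history between the groups.

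**Direction is unknown.** This is correct. A reader might infer that the crude test must favour waiting. The documents do not support that, because the background suggests that some higher-risk patients would wait, which would work against the hypothesis.

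**Instruments.** A reader might combine the free choice of technique with the background's statement, on cold knife against electrocautery, that "the latter reduced the incidence of intrauterine adhesions by 90% after surgery", and derive a very large bias. The documents do not support that step. The background gives the figure for intrauterine diseases generally, and the title of reference 19 names septum, adhesions and submucosal fibroids. Electrocautery is not recommended in section 4.2.2, and nothing gives its share by group. Some expectant patients may expel the tissue and have no operation. Technique is also chosen after grouping, so it may partly lie on the causal path and is not a baseline confounder.

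**Small centres.** Twelve centres average 40 patients, about 40 × 0.098 = 4 adhesions each before dropout. Adjustment within each centre is likely to fail. This limits how centre can be handled but does not justify ignoring it.

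**Conclusion.** The point holds. The stated analysis of the primary outcome is a crude test of self-selected groups, and the stated bias control does not touch confounding. Followed as written, the plan cannot separate the effect of waiting from the effect of who chose to wait.

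The size is not known from the documents. In the table above, false rejection runs from 6% to about 20–21%, or power falls from 91% to between 88% and 67%. Stronger assumed imbalance takes false rejection as high as 66%. These figures rest on one assumed binary factor, equal groups of 230 and the planning rates. They show what can happen and do not estimate the bias in this study. The sample-size arithmetic is correct, but its 90% power applies to the unadjusted comparison only.

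This should be corrected before the groups are compared, because it concerns the primary outcome and the remedy uses data already being collected.

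**What to change.** 1. **Primary analysis.** In section 8, name a covariate-adjusted risk difference in adhesion incidence with 95% CI, for example from propensity-score weighting. With about 45 events expected, weighting is easier to support than an outcome regression with many covariates.
2. **Covariates.** Age, parity, previous intrauterine procedures and adhesion history (section 5.1); gestational age at termination; time from termination to first visit; and first-outpatient-visit HCG and ultrasound values (section 4.3.1): lesion diameter, blood-flow grade, internal os-to-fundus length and suspected accreta. Do not use values measured after the waiting period. Section 5.2 is headed as preoperative, and in expectant patients surgery follows waiting until HCG, os-to-fundus and blood-flow thresholds are met (section 4.1.2), so those values may already reflect the strategy.
3. **Centre.** Account for it in the model or the standard errors, not by weighting within each small centre.
4. **Checks.** Report overlap and covariate balance before and after weighting.
5. **Crude test.** Keep chi-square or Fisher as a descriptive result.
6. **Technique.** Use it only in a sensitivity analysis, because it is chosen after grouping.
7. **Section 9.2 and section IV.3.** Add confounding to bias control, and say that the 90% power refers to the unadjusted comparison.

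**Cost.** Wording and programming, with no new data and no change to care. Some precision is lost: under assumed R² of 0.05 to 0.20, 460 evaluable becomes about 485 to 575, against about 480 expected from 600 enrolled. Adjustment removes only measured confounding, and the report should say so.
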